3.6 STUDY PROCEDURE

The study will use the precede proceed planning model and the ecological model described in the review of Literature following the steps below from planning the research project, through implementing the intervention, and to the monitoring and Evaluation phases.

Step 1: Preparatory/Planning Phase

The planning model to use here will be the Ecological model in conjunction with aspects of the PRECEDE-PROCEED planning model (PPPM).

The other steps of the planning phase include:

- Preparing documents to apply for ethical clearance and administrative authorizations to perform the study.
- Authorizations are needed from the Regional Delegation of Secondary Education for the SWR (1), the divisional delegates/inspectors of the aforementioned ministry (2), the School Principals (8) the Regional Delegation of Public Health

(RDPH) for the SWR (1), and the Chiefs of Health Districts (CHDs) (2)

- Constitute and train a team of 4 trainers medical doctors/students and data collectors and interviewers.
- Obtain a sample frame of students from the various classrooms of the various schools and proceed with the selection of participants as described above.
- Enlist all potential teachers and stakeholders to be interviewed

Step 2: Intervention Phase

- Organize students to be trained in groups of 10.
- Each training session will last 2.5 hours and each group will be trained for 2 days.

That is a total of 5 hours.

- Overall, it will take 6 weeks (1 month, 2 weeks) to train 3 groups of 25 students each as shown in *Table 6* below.
- The Sessions will begin with a 30-to-45-minute pretest followed by theory on day 1. Then mixed theory, video, and practical sessions on days 1 and 2. Main contents Content include: 1. responding to emergencies (first aid) and on prevention of injuries: “Call for help”, fever and contents of a first aid kit, 2. controlling Life-threatening bleeds (LTBs) and immediate first aid in burn cases, fractures, and/or dislocations in the face of LTB [11,46]. It will include the use of cartoons, simple language and memory aids:

(1) Video, (2) small group teaching, (3) demonstration manikin, (4) supervised practice.

- Interviewing the teachers, principals and other stakeholders. Interviews will be done using interview guides and tape recorders.
- For the control group, we will do a selection of the participants as described and there

will be a session for pretesting at the beginning of the intervention, at the immediate end, and 3 months after. **During the 3 months follow up period, we will visit the schools during their Wednesday club days every 2 weeks for 30mins to 1hour, to document their experiences and challenges in real time and their use of the skills.**

The qualitative part will take place before the quantitative pretesting of both groups begins.

Table 6: Plan of training and Evaluation of intervention groups

HA	School	N	Training Period in 2024	Date for Last Evaluation, 2024
Molyko (Intervention)	BGS Molyko	25	Nov 6 th , and 13 th	Feb 5 th
		25	Nov 20 th , and 27 th	Feb 19 th
		25	Dec 4 th and 11th	March 5 th
Mutengene (Control)	GHS Mutengene	70	November 6 th	Feb 26 th
	Total	145		

Step 3: Evaluation Phase

This comprises the evaluation of students' perceptions, barriers, and challenges in learning and applying the skills and lessons learned. It will equally involve evaluating parents' and stakeholders' perceptions about the program and including FA training in school curricula. It will involve the use of evaluation forms. This will take place about the same time as the post-three-month evaluation.

Knowledge will be assessed by evaluating whether the participants have ever heard of first aid or observed situations in which first aid was needed. They will be expected to have an increase in knowledge of first aid, especially regarding calling for help, stopping acute and life-threatening bleeds (LTB), and referrals after the training.

Before the training, we expect people not to have practiced first acts ever or to have

done it in a wrong way or to be scared to carry out specific first aid acts. After the training, we expect them to be more alert and identify situations needing first aid acts. Additionally, we expect their self-efficacy and confidence to perform first aid acts to increase and to effectively carry out first aid acts within their community or the school premises that will be documented using designed forms.

We will consider criteria for success as the proportion of persons who made an emergency call to an adult, teacher, the emergency number of the regional hospital, to a medical professional or to the closest Health Facility to the incident. The proportion of people who received help. The proportion of persons whose bleeds or LTBs were alleviated or attended to or who were referred for better management. Furthermore, the intention to treat/carryout the desired first aid act in the phase of an acute incident requiring FA. Lastly, we would like to evaluate the number of students who perform well during the scenarios to evaluate the need for knowledge revamping/refresher course on the aspects of FA taught. And all these, we shall compare the outcomes between the intervention and control groups.

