3.7 STUDY VARIABLES AND TYPE

Variables

Outcome variables

1. Knowledge Change: to determine whether or not there was an overall change in knowledge before and after the training (dichotomous).
2. Test scores: to measure the educational efficacy of the first aid training before and after the intervention in comparison with the control group (continuous)
3. Self-efficacy ratings: Participants' self-perceived efficacy in performing first aid skills or their confidence levels in "Stopping the bleed and/or calling for help" (dichotomous)

4. Response time: The time taken by participants to respond to simulated first-aid scenarios or emergencies that require them to either stop an LTB or call for help or refer (continuous).
5. The number of participants who make use of the skills taught during the 3 months post-training but before the final assessment (Discrete).

Exposure Variables

The exposure variables include training on LTBs from injury first aid and the use of these services by the trained students (e.g., the number of persons assisted or referred during the follow up period of the training).

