3.11 DATA ANALYSIS PLAN

A difference-in-difference analysis would be done to assess the change in KAPs before and after the intervention in. The posttest would be done immediately after the 4 days of training for each pool and 3 months after the training to assess the need for refresher course planning.

The exposure variables include training on LTBs from injury first aid and the use of these services by the trained students (e.g., the number of persons assisted or referred during the follow-up period of the training).

We will analyze survey data using R Software with a combination of descriptive statistics and parametric and non-parametric tests to establish statistically significant differences between pre- and post-test results and between the intervention and control groups.

Table 7: Objectives and their Indicators

Objective	Activities/process	Data collection tools	Data Source	Indicators
1. To understand the perspectives of stakeholders on YoFA training program among SSC	- In-depth interviews	-In-depth interview guides	School teachers, administrators, parents, community leaders and students	
2. To assess school children's KAP (willingness and self-efficacy on trauma/injury FA via the built YoFA training to stop LTBs.	- survey	-Questionnaire	- students	- Obtain baseline KAP Scores
3. To evaluate the effectiveness and usability of the YoFA training program for SSC to respond to LTBs safely and promptly in their environs.	-Training following a specific STB and LFRs program -Training students on specific modules of LTB FA - Pre and post test -Simulation exercises	- Use adapted tools from the SBEAT - Questionnaires - Evaluation form with questions how? What was the situation?where, and how?	Stakeholders, teachers, parents, students	- Change in knowledge scores -At least 50% of stakeholders rate the program as good/ expectations met - 70% of students rate the program as good/expectations met - Number of children who made use of the FA skills taught
4. To determine the barriers associated with implementing the YoFA program among early SSC in the Fako Division.	- Interviews - Survey	-Interview guides - Questionnaires	- Stakeholders, - Teachers, students	- Perceived reasons and challenges that hinder FA training in schools.

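### Table 6 gives the control class 112 days from pretest to last evaluation against 91 in every trained wave, and no date for its immediate post-test (minor; cheap to correct)

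*Protocol*

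**What the plan says.** Protocol section 3.6, Step 2, sets the trained pupils' baseline on the first day of their wave: "The Sessions will begin with a 30-to-45-minute pretest followed by theory on day 1". Table 6 lists three waves at the intervention school, with training on "Nov 6 th , and 13 th", "Nov 20 th , and 27 th" and "Dec 4 th and 11th", and last evaluations on 5 February, 19 February and 5 March. The control school is a single block of 70 pupils with one November date, the 6th, and a last evaluation on 26 February.

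For controls, section 3.6 says there "will be a session for pretesting at the beginning of the intervention, at the immediate end, and 3 months after". Table 6 has no entry for the middle test.

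Section 3.11 names a difference-in-difference analysis of the change in knowledge, attitudes and practices. On timing it says "The posttest would be done immediately after the 4 days of training for each pool", with a further test "3 months after the training to assess the need for refresher course planning". Section 3.7 lists among the outcomes "The number of participants who make use of the skills taught during the 3 months" following training. The success criteria in section 3.6, Step 3, include calls for help and bleeds attended to, and are to be compared between the groups.

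**The concern.** A difference-in-difference subtracts the control group's change from the trained group's change. It relies on the two groups changing alike, absent training, over the same stretch of time. If one group is followed for longer, part of the contrast may reflect the calendar.

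Some measures here depend directly on elapsed time. The questionnaire in section 3.8 asks whether the pupil has heard of first aid (item 5), has ever seen a traumatic injury (item 6), and has tried to stop a bleed and how often (item 8). Extra days can only add to such answers. The same holds for counts of calls made or bleeds attended to. Scored knowledge items are less exposed.

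The undated control post-test is a second gap. Until it has a date, the comparison at the immediate post-test has no defined interval in the control arm.

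**Working it through.** **Inputs.** All dates come from Table 6 in section 3.6. The table heads the last-evaluation column 2024. The training is in November and December 2024 and the study runs to July 2025, so February and March are read as 2025. The pretest is taken as day 1 of each wave (section 3.6). For controls it is taken as 6 November, the only early date given, which is also the day training begins.

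**Trained waves.** Days = later date minus earlier date.

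| Wave | Session 1 (pretest) | Session 2 | Last evaluation | Session 1 to 2 | Session 2 to last | Pretest to last |
|---|---|---|---|---|---|---|
| 1 | 6 Nov | 13 Nov | 5 Feb | 7 | 84 | 91 |
| 2 | 20 Nov | 27 Nov | 19 Feb | 7 | 84 | 91 |
| 3 | 4 Dec | 11 Dec | 5 Mar | 7 | 84 | 91 |

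The three waves reproduce the stated three months: 84 days from the last session, or 91 from the pretest. The schedule is identical in all three.

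**Control class.** 6 November to 26 February is 112 days. The excess is 112 − 91 = 21 days, and 21 / 91 = 23%.

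**The missing control post-test.** Its two gaps must add to 112 days:

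| Assumed control post-test | Pretest to post-test | Post-test to last |
|---|---|---|
| 13 Nov (end of wave 1) | 7 | 105 |
| 27 Nov (end of wave 2) | 21 | 91 |
| 4 Dec | 28 | 84 |
| 11 Dec (end of all training) | 35 | 77 |

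The trained gaps add to 7 + 84 = 91. Since 112 is not 91, no control post-test date can match both gaps at once. One gap can match: the first on 13 November, the second on 4 December.

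**Sensitivity to the trained post-test date.** Section 3.11 speaks of four training days, while Table 6 lists two dates per wave. If the trained post-test fell on some day other than the second session, the split of the 91 days would change. The 91-against-112 comparison would not, because it uses only the pretest and the last evaluation.

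**Calendar position.** The control's last test is 21 days after wave 1's, 7 days after wave 2's and 7 days before wave 3's. The waves' mean dates are 20 November (pretest), 27 November (second session) and 19 February (last evaluation).

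**The case against.** The strongest reply is that the calendars overlap and the offset is small. The control pretest falls on the first training day, as section 3.6 intends. The control's last test lies inside the trained range of 5 February to 5 March, 7 days from its mean. Controls receive no training before their last test, because section 3.12 places retraining after the study, so little background gain in knowledge over three weeks is plausible. With one school per arm (Table 5), a 21-day offset is also a minor part of what threatens the comparison. All of this stands, and it keeps the point minor. It does not explain why the control row alone departs from a schedule that is otherwise uniform.

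Three stronger readings are tempting, and the protocol does not support them:

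- A reader might infer that 112 days contradicts the stated three months. The three months run from the end of the intervention or training, whereas the 112 days run from the pretest. The control's own end date is missing, and the follow-up gap could be 84 or 91 days. The section 3.6 sentence also concerns controls only.
- A reader might set 112 control days against the 84 trained days after the last session and report a 33% longer window for skill use. That counts one arm from pretest and the other from the end of training. From pretest in both arms the excess is 23%. Section 3.7 defines the outcome over a nominal three months after training, so a 112-day control window is not stated anywhere.
- A reader might infer that the schedule flatters the programme. More time for controls to accumulate events would shrink the apparent benefit.

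**Conclusion.** The point holds as a minor one. The pretest-to-final change is measured over 112 days in controls and 91 days in every trained wave, a difference of 21 days or 23%, and this does not depend on where the missing control post-test is placed. The interval from post-test to final test cannot be judged until that date is given.

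The conclusion assumes that the February and March dates are in 2025, that 6 November is the control pretest, and that trained pupils are pretested on day 1 of their wave. The protocol gives nothing from which to compute the size of any bias. It is probably small for scored knowledge items. For items on whether something has ever happened, and for counts of first-aid acts, the longer control window would tend to hide a benefit.

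**What to change.** In Table 6, add a date for the control's immediate post-test and give the control class the trained waves' intervals. One set of dates is pretest 20 November, post-test 27 November and last evaluation 19 February. These are the mean dates of the three waves and give 7 and 91 days. State in section 3.7 that use of skills is counted over the same number of days in both arms, and say from which date the control count starts.

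The cost is that all three control tests then fall on the same days as wave 2's two sessions and its last evaluation, at a school in another district. Table 6 already schedules both schools on 6 November, so same-day work at two sites is part of the plan, but data collectors would have to be divided on three days. Waves 1 and 3 would still be tested 14 days either side of the controls.

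Two alternatives also equalise the intervals. If 26 February must stay, because no trained wave is evaluated that day, a pretest on 27 November and a post-test on 4 December give 7 + 84 = 91 days; those two dates coincide with sessions of waves 2 and 3. Or the 70 control pupils can be split at random into three sets tested on the three waves' dates, at the price of two extra visits to the control school per test round.

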3.3 STUDY DESIGN

This research will utilize a mixed-methods exploratory sequential design, incorporating both quantitative surveys and qualitative interviews. Exploratory because aspects of the qualitative aspects will be used to adjust the design of the YoFA training program which

will help develop a comprehensive program for such a program among SSC. The next design is a cross-sectional design with pre and post-tests to both the interventional and control groups to obtain a general baseline in both districts and assess the impact of the YoFA program.

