3.5 SAMPLE SIZE AND SAMPLING

Sample Size Calculation

For the cross-sectional study and Intervention

Assuming an equal number of control and intervention subjects, a prevalence of the outcome in the controls of 0.5, and a prevalence in the intervention group of 0.75 (an absolute increase of 25%)[17] with a power of 80% and 5% error margin, we calculated the sample size needed using STATA.

Estimated sample sizes for a two-sample proportions test Pearson's chi-squared test using STATA

$H_0: p_2 = p_1$ versus $H_a: p_2 \neq p_1$ Study parameters:

```
alpha = 0.0500
power = 0.8000
delta = 0.2500 (difference)
p1 = 0.5000
p2 = 0.7500
```

Estimated sample sizes:

N =	116
N per group =	58

If we assume a 15% drop out rate, we have a sample size of $15\% * 116 = 17.4$ Thus, sample size is $116 + 17.4 = 133.4 \approx 134$

For each group, the sample needed is therefore **N = 67 students. Sampling**

Since this is a crisis area, we will use convenience sampling to choose the Health Areas (HAs) that are secure and geographically accessible (safest) in both HDs. Out of seven (7) and eight (8) HAs in Buea and Tiko HDs respectively, there are 4 accessible HAs in each. Of these, one HA from each HD does not harbour a state secondary school (SSS).

Leaving us with 3 HAs to work with in each HD. Each of these HAs contains 1 SSS but for 1 HA from each District which has 2 SSSs. We would work with all these State schools to ensure that we get students from most of the communities around the schools, thus ensuring the representativeness of our samples. To avoid spill-over, one of the districts will be selected as intervention HD and the other as the control.

Stratified random sampling will be used to select the students for the study from a sampling frame of the list of students in each classroom concerned.

We would use probability proportionate to size to choose the specific number of students to participate in the study per classroom (A, B, and C) for each class.

[figure not shown]

Figure 5: Selection of HAs and Schools for Implementation.

*GHS-Government High School; BGS-Bilingual Grammar School; GTHS Government Technical High School; GBHS government Bilingual High School

For each school distribution of the participants will be as follows:

A) For the Qualitative part:

The qualitative part will be sampled purposively.

Table 2: Number of Participants to be chosen per school for the FGDs

Health District	Schools	FGD Category of Participant	Number per school

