3.8 DATA COLLECTION TOOLS

A) Questionnaire

**Pre- and Post-Implementation of a Young First Aiders (YoFA) Training
Program Amongst Early Secondary School Children on Injury and Trauma
First Aid in Fako Division.**

Health District _____
Secondary School _____

Date: _____
Class: _____

A) QUESTIONNAIRE

Section 1

Please answer the questions below by **ENCIRCLING OR WRITING** the right answer you think is correct. If you do not know an answer, please select the answer you think is correct.

1. Gender	YES	or	NO
2. Age (in years):	_____		
3. Parents' Occupation:	Father _____ Mother _____		
4. Do you have access to a mobile phone all the time?	YES	or	NO
5. Have you heard the words First Aid?	YES	or	NO
6. Have you ever seen a traumatic injury? (A traumatic injury is an injury you sustain when something outside your body causes you to lose function or render you unable to use part or all of your body because of pain, bleeding or the because it is very serious)	YES	or	NO
7. A) Have you ever received any training in First Aid (formal or informal)?	YES	or	NO
B) If yes, briefly describe the training (where was it, what did you learn? How long ago was it?)			
Where? _____			
How long ago?			

 a) < 6months ago b) 6 to less than 12 months ago c) 1 to 3 years ago d) >3 years ago 			
What you learnt? _____			
<hr/>			
8. Have you ever seen someone bleeding and tried to stop that bleed yourself at home, school, marketplace, or anywhere else?	YES	or	NO
B) How many times has that happened? (Choose one)			

 a) Never b) Just once c) 2 to 5 times d) >5 times 			

C) What did you do to stop the bleeding? _____ **YES** or **NO**

D) Did it work? **YES** or **NO**

9. **A) Do you remember watching other people do this in the past?** **YES** or **NO**
B) Have you ever watched someone else offer such help in question 5? **YES** or **NO**

10. **If you find someone bleeding today,** **YES** or **NO**

A) Will you help them?

B) If 'no', why will you not help?

- I don't know what to do
- I am afraid I will make it worse
- I am afraid I will get into trouble
- I am afraid of blood
- Other reason _____

C) If 'yes', why will you help? _____

D) What steps will you take to help if 'yes'?

- Help by putting in toothpaste
- Help by applying pressure on the wound
- I will not help
- I will call an elderly person.

[figure not shown]
B) If you would not help, what makes you not want to help?

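### Section 3.6 assesses knowledge by past exposure to first aid, contradicting the test score used elsewhere; secondarily, where scenarios take place needs reconciling with the promised between-arm comparison

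*Protocol*

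**What the plan says.** **Knowledge.** Section 3.6, Step 3, gives this rule: "Knowledge will be assessed by evaluating whether the participants have ever heard of first aid or observed situations in which first aid was needed". The next sentence there expects knowledge to rise after training on calling for help, stopping bleeds and referral.

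Section 3.7 lists two knowledge-related outcomes. Outcome 1, Knowledge Change, is "to determine whether or not there was an overall change in knowledge before and after the training (dichotomous". Outcome 2, Test scores, is "to measure the educational efficacy of the first aid training before and after the intervention in comparison with the control group (continuous".

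Section 3.3 gives "pre and post-tests to both the interventional and control groups". The questionnaire in section 3.8, headed "Pre- and Post-Implementation of a Young First Aiders (YoFA) Training", asks at item 5 "Have you heard the words First Aid" and at item 8 "Have you ever seen someone bleeding and tried to stop that bleed yourself". Item 6 asks whether the pupil has ever seen a traumatic injury. The questions with right and wrong answers are items 13 to 37.

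**Scenarios.** Section 3.6, Step 3, counts pupils who do well in the scenarios among its success criteria and says all the criteria will be compared between the two groups. It places this phase at about the time of the 3-month evaluation. Section 1.1.2 defines injury response time by timing pupils in simulated emergencies in training sessions. Response time is outcome 4 in section 3.7.

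**The concern.** Whether a pupil has ever heard of first aid, or ever seen a situation calling for it, says nothing about whether the pupil knows what to do. A truthful yes to an *ever* question cannot later become no, and the pretest itself supplies the exposure in both arms. Anyone who applied the section 3.6 sentence as written would have a knowledge measure that cannot show a training effect and could show a spurious one if the two schools differ at baseline.

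The scenario point is smaller. If scenarios are run only where section 1.1.2 places them, the control arm has no scenario or response-time data, and the comparison promised in section 3.6 cannot be made. Data not collected at the 3-month visit cannot be recovered at the analysis stage.

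**Working it through.** The plan attaches no figure to the exposure rule, so there is none to reproduce.

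**Definitions of knowledge, side by side (Protocol).**
- Section 1.1.2: understanding of basic principles on a standardised questionnaire, before and after training.
- Section 3.7, outcome 2: a continuous test score, before and after, against control.
- Section 3.9: multiple-choice pre- and post-tests adapted from the Stop the Bleed assessment tool.
- Section 3.11, Table 7, Objective 3: change in score.
- Section 3.6, Step 3: ever heard of first aid, or ever observed a need for it.

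The first four agree and the fifth does not. It matches background items 5 and 6 of the questionnaire, not items 13 to 37.

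**What the exposure rule yields.** Assumptions: every pupil sits the pretest and answers truthfully. The rule joins its two parts with *or*, so having heard of first aid is enough for a yes.

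Let bT and bC be the baseline proportions answering yes in the intervention and control arms.
- Status after the pretest: 1.00 in each arm.
- Change in the intervention arm: 1 - bT. Change in the control arm: 1 - bC.
- Difference-in-difference: (1 - bT) - (1 - bC) = bC - bT.

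The protocol gives no baseline values, so these are illustrations only:

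| bT | bC | Change, intervention | Change, control | Difference-in-difference |
|---|---|---|---|---|
| 0.60 | 0.70 | 0.40 | 0.30 | +0.10 |
| 0.70 | 0.60 | 0.30 | 0.40 | -0.10 |

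No term for the training appears in the formula. If the *observed* part were counted alone, it need not reach 1.00, but it would record which incidents pupils had met or noticed, which is still not understanding.

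**Scenario passages, side by side (Protocol).**
- Section 3.6, Step 3: scenario performance is compared between arms, in a phase set at about 3 months.
- Section 3.2: the evaluation involves all the students, in wording that can be read as covering both groups.
- Section 3.3.2: scenarios test participants; neither arm nor time is named.
- Table 7: simulation exercises are listed under Objective 3; again neither arm nor time is named.
- Abstract and section 3.9: scenario observation or a simulation exercise appears under qualitative data.
- Section 1.1.2: response time is taken in training sessions, and practical skill is rated by the trainers.
- Section 3.6, Step 2: control sessions are described as test sessions at the start, the immediate end and 3 months.

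The first two point to both arms at 3 months. Section 1.1.2 points to the trained arm during training. For response time both cannot hold as written.

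**The case against.** **Loose wording.** The sentence after the disputed one expects gains in content that items 13 to 37 test, and four other places define knowledge by test. This is fair, and it is why the score comparison is not in doubt. But the sentence says how knowledge will be assessed, and as a rule it is wrong.

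**Knowledge Change.** A reader might infer that the exposure rule defines this dichotomous outcome, because it is the only yes/no knowledge criterion in the protocol. The documents do not make that link. The outcome reads naturally as derived from the pre/post test, and its cut-off may properly sit in a statistical analysis plan. Even under the exposure rule, a change outcome would have proportions 1 - bT and 1 - bC. The figure of 1.00 in both arms is post-test status, not change.

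**Sample size.** A reader might set those proportions beside the design assumption of "a prevalence of the outcome in the controls of 0.5, and a prevalence in the intervention group of 0.75". Section 3.5 names no outcome for those figures, so nothing follows about the sample size.

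**Scenarios.** A reader might infer that controls get no scenario. That is not shown. The 3-month timing of the Evaluation Phase, its between-arm promise and section 3.2 together allow a scenario in both arms. Doing well in a scenario is also a different measure from response time, so section 1.1.2 does not directly contradict the count of good performers. What stands is the mismatch over where scenarios take place and where response time is measured.

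**Conclusion.** The knowledge point holds. Section 3.6 contains a rule that measures exposure and conflicts with four other places in the protocol. Given a pretest in both arms and truthful answers, its difference-in-difference is bC - bT, which is baseline imbalance alone. The size depends on baselines the protocol does not give; the +0.10 and -0.10 above are illustrations. The reach is limited: the test-score comparison stands, and no consequence for Knowledge Change or the sample size is established.

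The scenario point holds as a secondary inconsistency. The documents do not show that a control scenario is absent, but sections 1.1.2, 3.2 and 3.6 need to agree before the 3-month visits. Both points warrant correction; neither undermines the main comparison.

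**What to change.** **Knowledge.** Delete the exposure sentence in section 3.6, Step 3. State there that knowledge is the pre/post score on the knowledge items (for example items 13 to 37, saying whether item 10D is scored), at the same time points in both arms. In section 3.7, say that Knowledge Change is derived from that score by a rule fixed in advance. Keep items 5, 6 and the seen or watched parts of items 8 and 9 as baseline descriptors. The cost is wording in two sections.

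**Scenarios.** Reconcile sections 1.1.2, 3.2 and 3.6 in one of two ways.
- *Both arms:* state that the same scenario is run in both arms at the 3-month evaluation, and name the raters. At an assumed 2 to 5 minutes per pupil, the 140 pupils of Table 5 need 140 x 2 = 280 minutes (4.7 hours) to 140 x 5 = 700 minutes (11.7 hours) of team time. This gives a post-only contrast between two schools, with raters likely to know the arm.
- *Trained arm only:* remove scenario performance and response time from the between-arm comparison and report them descriptively. The cost is wording, and the between-arm skills result is given up.
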